Asthma is a chronic inflammatory disease characterized by pulmonary inflammation and bronchoconstriction, with the prevalence of asthma steadily rising worldwide¹. **Asthma and Cardiovascular Disease:** While asthma is generally considered to be a disease of the airways, there are important systemic consequences which have predisposed people with asthma to become more likely to die from cardiovascular (CV) disease compared to non-asthmatics². Additional CV risks have been reported in people with severe asthma³, and there is a relationship between reductions in lung function and cardiac death⁴. To date, little is known in regards to the interaction between asthma exacerbations and CV risk. **Asthma and vascular dysfunction:** Brachial flow-mediated dilation (FMD) is used as a non-invasive tool to evaluate endothelial function⁵. Brachial FMD is impaired in people with coronary dysfunction⁶, and can predict future CV events better than traditional CV risk factors⁷. People with asthma have previously been shown to have impaired endothelial function compared to non-asthmatics⁸, but the underlying mechanism(s) are unclear. **Asthma, systemic inflammation, and CV risk:** Chronic systemic inflammation is an established risk factor and predictor of future CV events⁹, and levels of systemic inflammation are increased in asthma^{10,11}. Furthermore, while people with high levels of inflammation are more likely to suffer both first time and recurrent cardiac events^{12,13}, levels of systemic inflammation in asthma are related to disease severity and are the highest during asthma exacerbations^{10,11}. Previous studies have shown that systemic inflammation directly impairs vascular function¹⁴, and rodent work has shown that pulmonary inflammation can impair vascular function¹⁵. To-date, no study has examined how an asthma attack may affect vascular function and CV risk. Thus, to gain better understanding of the increased CV risks associated with asthma exacerbations, *the aim of this study is to evaluate vascular function and systemic inflammation during a naturally occurring asthma exacerbation.*

If this study finds a large systemic inflammatory insult as well as significant vascular dysfunction, as a result of an asthma exacerbation, this could have strong clinical implications. This research would highlight the importance of preventing an asthma exacerbation based on the significant negative impact that an acute exacerbation may have on the cardiovascular system. Future research on pulmonary rehabilitation for asthma could target reducing systemic inflammation and improving vascular function, as well as changes to current guidelines and recommendations for people with asthma to reflect the necessity of reducing systemic inflammation and improving vascular function to reduce CV risk.

2 Study Objectives

Primary Objective

To examine the endothelial function of an individual experiencing a naturally occurring asthma exacerbation.

Secondary Objective

To examine the arterial stiffness and systemic inflammation of an individual experiencing a naturally occurring asthma exacerbation.

3 Patients and Methods

3.1 Study Design

3.1.1 General Design

This study is a cohort study utilizing a repeated measure design. Asthmatic patients will be tested at 3 different time points:

- At the emergency department
- 48 hours following discharge
- 14 days following discharge

Stable asthmatic and non-asthmatic controls will be tested at two time points:

- Day 1
- 48 hours following Day 1

Vascular parameters such as flow mediated dilation (FMD; endothelial function) and pulse wave velocity (PWV; arterial stiffness) will be evaluated at each time point to assess vascular function. Blood samples will be obtained for analysis of systemic inflammatory response and immune response at each time point.

Participants will also be given Fitbit activity monitors for 7 days of monitoring, perform a full pulmonary function test (PFT) and complete 3 questionnaires; Asthma Control Questionnaire (ACQ), Asthma Quality of Life Questionnaire (AQLQ), and EQ-5D.

(A) Cohort studies

Definition of study groups:

Individuals experiencing an asthma exacerbation will be identified at the University of Alberta Emergency Department (ED). They will be recruited based on asthma being the primary physician diagnosis in the ED, with asthma being confirmed at a follow up visit using spirometry.

Stable asthmatic controls will be recruited from the general populations, as well as two local pulmonary clinics: The Lung Health Clinic, Edmonton, AB; and the University Lung Clinic, Edmonton, AB. These participants will be recruited if they have indicated they have been diagnosed with asthma. Both confirmed and unconfirmed asthmatics will be eligible.

Healthy controls will be recruited from the general population. They will be age-, sex, and BMI matched to the exacerbation group.

Blinding and avoiding bias:

Due to the nature of the study, blinding will not be applicable.

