Controls are being tested at two times to determine the degree of natural fluctuations in endothelial function, arterial stiffness, and systemic inflammation in healthy adults.

Measurements

Waist Circumference – Using a fabric tape measure, waist circumference will be measured at the level of the last rib to the nearest 0.1 cm after a normal expiration.¹⁷ This will be used as a measure of adiposity and will potentially be used as a covariate during statistical analysis.

Arterial stiffness - Arterial stiffness will be evaluated using pulse wave velocity (PWV) between the carotid and femoral arteries. After 10 minutes of resting in a dark, quiet room in the supine position, cPWV and pPWV will be recorded using applanation tonometry (Complior, Alam Medical, Saint Quentin Fallavier, France). A series of 10 consecutive beats will be taken with a minimum quality of 85%. The distance between the carotid and femoral artery, as well as the carotid and radial artery will be recorded in mm. PWV will be measured prior to FMD and blood collection, and will be taken on all 3 days of assessments. PWV is expressed as m/s and is calculated as $PWV = L/\Delta t$, with L being the distance between the two points and Δt being the time it takes for the pulse to get from site 1 to site 2.²²

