3.4 Statistical Plan

3.4.1 Sample Size Determination

While the impact of asthma exacerbations on vascular function is currently unknown, we based our sample size calculation on our preliminary VTI data from 11 confirmed asthmatics who underwent a mannitol airway challenge to induce airway inflammation and bronchoconstriction. Based on these data, a total of 36 asthmatics and 36 controls in each group (stable asthma, healthy) would be sufficient to detect a 13% difference between these groups in VTI. Our preliminary data show a large increase in CRP in asthmatics experiencing an exacerbation vs. stable patients (7.3 vs. 0.5 mg/L, $p<0.05$), which would correspond to a substantial increase in CV risk³⁵, and be detectable with this sample size. An additional 8 participants per group will be recruited (i.e. 44 asthmatics, 44 stable asthmatics, and 44 controls) to compensate for potential dropouts. Sub-analyses evaluating potential sex-based differences will be exploratory and results will be considered hypothesis-generating.

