3.4.2 Statistical Methods

The mean differences in FMD, systemic inflammation, and arterial stiffness for ED visit compared to the control group will be evaluated using an unpaired t-test. A within-factors repeated measures analysis of variance (ANOVA) will evaluate the mean differences between each assessment day for the exacerbation group to assess change in endothelial function during exacerbation as well as the recovery period. A similar evaluation will be used for arterial stiffness and systemic inflammation/immune response. A one-way analysis of covariance (ANCOVA) will be used to correct for shear rate in FMD for all groups, with both values being reported. An α -level of 0.05 will be used as the significance level for all statistical analysis, and all results will be reported as mean \pm standard deviation unless indicated otherwise.

4 Data Handling and Record Keeping

Data to be collected:

Outcome variables:

Endothelial function

Source of the data: Flow-mediated dilation test (see *measurement, endothelial function* above).

Time point for collection: Collected as the last assessment during the ED visit. For the 2 follow up visits, FMD will be done after arterial stiffness and prior to blood draw.

Who will collect the data: All data will be collected by trained research staff associated with the study.

Why the data is being collected: To evaluate the influence of acute asthma exacerbation on vascular health.

Is the data from a standardized tool: Yes.

What form will the data will take (e.g. binary, continuous (numeric), time to event): Continuous.

Arterial stiffness

Source of the data: pulse wave velocity test (see *measurements, arterial stiffness* above).

Time point for collection: At the ED, arterial stiffness will be collected after blood draw and prior to endothelial function. At the follow up visits, it will be collects as the primary assessment.

Who will collect the data: All data will be collected by trained research staff associated with the study.

Why the data is being collected: To evaluate the influence of acute asthma exacerbation on vascular health.

Is the data from a standardized tool: Yes.

What form will the data will take (e.g. binary, continuous (numeric), time to event): Continuous.

Systemic inflammation and immune response

Source of the data: Venous blood samples (see *measurements, systemic inflammation and immune response* above).

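### The test against healthy controls ignores the age, sex and BMI matching, and forgoes power to the extent that those factors predict the outcome

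*Combined protocol and SAP*

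**What the plan says.** - **Matching (3.1.1, definition of study groups).** Of the healthy controls: "They will be age-, sex, and BMI matched to the exacerbation group". The section does not say whether matching is one-to-one or by frequency, and gives no tolerance or ratio. It states no matching for the stable asthmatics.
- **Between-group test (3.4.2).** The ED-visit means of FMD, systemic inflammation and arterial stiffness "compared to the control group will be evaluated using an unpaired t-test". Which of the two control groups is meant is not stated.
- **Planned adjustment (3.4.2).** "A one-way analysis of covariance (ANCOVA) will be used to correct for shear rate in FMD for all groups, with both values being reported". This concerns shear rate only, and FMD only. PWV and the biomarkers have no named adjustment.
- **Possible covariate (3.3, Measurements).** Waist circumference "will potentially be used as a covariate during statistical analysis". It is not a matching factor, and no model is named for it.
- **Main endothelial outcome (3.3, Endothelial function).** FMD corrected for shear stress.
- **Significance level (3.4.2).** A "level of 0.05 will be used as the significance level for all statistical analysis".
- **Size (3.4.1).** The plan holds that "a total of 36 asthmatics and 36 controls in each group (stable asthma, healthy) would be sufficient"; its target is a VTI difference of 13%.

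**The concern.** Matching makes the two groups alike on age, sex and BMI. If those factors influence the outcome, the group means move together and the difference between them varies less from sample to sample than it would between two independent samples. The unpaired t-test assumes independent samples, so the variation due to the matching factors stays in its standard error although matching has largely removed it from the difference itself. The test is then conservative. With only 36 evaluable participants per group, a real difference in FMD, PWV or a biomarker could be missed because of the choice of test, after the study has already borne the recruitment burden of matching on three variables.

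**Working it through.** **The plan's own figure.** The 36 per group in 3.4.1 can be neither reproduced nor refuted, because the SD, the power and the sidedness are not given. Taking a two-sided 0.05, 36 per group corresponds to a standardised difference of 0.66 at 80% power (a VTI coefficient of variation of 13/0.66 = 19.7%) or 0.764 at 90% power (13/0.764 = 17.0%). The dropout allowance adds up: 36 + 8 = 44. None of this depends on the matching.

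**Inputs.** From the documents: n = 36 per group and alpha = 0.05. Assumed: a two-sided test; close matching; the share R² of outcome variance explained by age, sex and BMI, taken as 0% to 30%; and a difference of 0.5 SD for power.

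**Formulas.** Let σ be the outcome SD within a group.

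- Standard error used by the unpaired test: σ√(2/n).
- Actual standard error under close matching: σ√(2(1 − R²)/n).
- Ratio of the two: 1/√(1 − R²).
- True size at nominal 0.05: 2[1 − Φ(1.96/√(1 − R²))].

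For example, at R² = 0.2 the ratio is 1/√0.8 = 1.118, and 1.96 × 1.118 = 2.19 gives a size of 0.028.

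| Assumed R² | Standard error too large by | True size, formula | True size, simulated | Power at 0.5 SD, unpaired | Power at 0.5 SD, adjusted |
|---|---|---|---|---|---|
| 0% | 0% | 0.050 | 0.050 | 0.55 | 0.55 |
| 10% | 5.4% | 0.039 | 0.038 | 0.55 | 0.60 |
| 20% | 11.8% | 0.028 | 0.030 | 0.56 | 0.65 |
| 30% | 19.5% | 0.019 | 0.021 | 0.56 | 0.71 |

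Simulated size is for one-to-one matched pairs at n = 36 (50,000 replicates). Unpaired power was simulated; separate runs gave 0.55 to 0.57. Adjusted power follows from the noncentral t with 72 − 2 − 3 = 67 degrees of freedom and noncentrality 0.5 × √18/√(1 − R²), and agrees with simulation to within 0.01.

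**Type of matching.** Frequency matching over eight strata gives the same pattern: size 0.051, 0.039, 0.028 and 0.020 for the unpaired test at R² = 0%, 10%, 20% and 30%. A model adjusted for the matching score gives 0.049 to 0.051. The result therefore does not depend on which type of matching 3.1.1 intends.

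**Loose matching.** If the matching scores of a pair correlate only at q, R² is replaced by q × R² in the size formula. With q between 0.5 and 0.8, size is 0.044 to 0.041 at R² = 10% and 0.033 to 0.025 at R² = 30%. The direction is the same and the effect is smaller.

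**A larger difference.** At 0.66 SD, which 36 per group detects with 80% power when R² = 0, normal-approximation power at R² = 10%, 20% and 30% is 81%, 83% and 84% unpaired, against 84%, 88% and 92% when the matching is used.

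**The case against.** The strongest reply is that nothing is lost against an unmatched study. Unpaired power at 0.5 SD is about 55% with no matching effect and 55% to 57% with one, so a gain is forgone rather than power destroyed; at 0.66 SD that gain is only about 3 to 8 percentage points. This stands, and it sets the weight of the point.

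Several stronger readings are tempting, and the documents do not support them:

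- **That the error rate is certainly below 0.05.** This needs age, sex and BMI to predict the outcome, and no figure is given. At a share of zero the size is exactly 0.05; at 5% it is 0.044. Eligibility (ages 18 to 55, known metabolic conditions excluded) may also narrow the spread of these factors.
- **That reported confidence intervals have the wrong coverage.** Section 3.4.2 plans tests and means with standard deviations; it promises no intervals.
- **That the matching buys no precision.** It does make the estimated difference more precise, and it controls confounding by the three factors. Only the estimated standard error fails to show the gain.
- **That the study-wide error rate is low.** The size above is per test. Many outcomes each tested at 0.05 push the overall error the other way.

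It is also fair to object that 3.4.2 does not name the control group. If only the stable asthmatics are meant, no matching is stated and the point does not apply to that test. Finally, the main endothelial outcome is shear-corrected FMD, which is handled by ANCOVA, so replacing the t-test alone would not reach it. The fix has to cover both.

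**Conclusion.** The mismatch is real: healthy controls are matched on three factors, and no planned analysis of that comparison uses them. Its consequence is conditional. With close matching, 36 per group and an assumed share of variance of 10% to 30%, the unpaired standard error is 5% to 20% too large, the true per-test size is about 4% to 2%, and power at an assumed 0.5 SD is 55% to 57% where 60% to 71% is available. With a share of zero there is no effect, and with loose matching it is smaller. The power and size figures are for an unadjusted continuous outcome; they were not computed separately for shear-corrected FMD, PWV or individual biomarkers.

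The harm is lost efficiency, not false positives. It is confined to exacerbation against healthy controls, and it leaves the repeated-measures analysis within the exacerbation group untouched. The change is worth making because it costs almost nothing, but the plan is not invalid without it.

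**What to change.** In 3.4.2:

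1. State that this comparison is exacerbation (ED visit) against healthy controls, and replace the unpaired t-test for it with a linear model for group that includes age, sex and BMI as covariates. Apply it to uncorrected FMD, PWV and the biomarkers.
2. For shear-corrected FMD, add the same three covariates to the planned shear ANCOVA, so that the uncorrected and corrected values are both adjusted for the matching factors.
3. In 3.1.1, state whether matching is one-to-one or by frequency. If it is one-to-one, a paired analysis can serve as the sensitivity analysis.

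The model suits either type of matching, keeps participants whose matched partner is lost, and corrects residual imbalance if matching is loose.

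**Cost.** A change of wording and three degrees of freedom (70 to 67 with 36 per group). No new data are needed: matching already requires the three variables for both groups, and the Appendix 5 form records sex, age, weight and height. If the factors turn out to explain nothing, power is essentially unchanged (0.55 either way at 0.5 SD).

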3.1.2 Primary Outcome Variable

Flow-mediated dilation (FMD) of the brachial artery following 5 minutes of forearm occlusion will be measured using our ultrasound machine (8L-RS 4.0-13.0 MHz probe, Vivid q, GE Healthcare, Mississauga, ON) and FMD data will be analyzed using FDA approved software available from Medical Imaging Applications (Coralville, IA, USA). FMD will be calculated as: (peak hyperemic diameter-baseline diameter)/baseline diameter x 100. Peak hyperemic brachial arterial velocity (and subsequently shear stress) will be determined using Doppler ultrasound, and used for normalization of FMD.

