Endothelial function - The endothelial function of the brachial artery will be evaluated after 10 minutes of rest in the supine position using ultrasound imaging (8L-RS 4.0-13.0MHz probe, Vivid q, GE Healthcare, Mississauga, ON). Baseline diameter of the brachial artery will be established, whereby the blood flow of the forearm will be occluded distal to the measuring site for the duration of 5 minutes. Upon release of the occlusion, the blood velocity and the brachial diameter will be monitored for 3 minutes, and later analyzed (Medical Imaging Applications, LLC, Coralville, IA, USA; EchoPAC PC software, version 110.x.x, GE Healthcare, Horten, Norway). Microvascular function will be evaluated as the velocity time integral-envelope of the first heartbeat of reactive hyperemia (VTI; m/s) and the velocity during reactive hyperemia (VRH) calculated as $VTI \times 60/HR$.²³ Shear stress during reactive hyperemia (SSRH) will subsequently then be calculated as $SSRH = 8 \times \text{flow} / \text{diameter}$ and as cumulative SSRH until the time of peak FMD%.^{24,25} FMD corrected for SSRH will be considered the main outcome for endothelial function in this study, and VRH and SSRH as indicators of microvascular function. Follow up tests will be conducted after a 12 hour fasting period when possible. Where applicable, the subjects will be asked to withhold any long-acting asthma medication for a minimum on 48 hours prior to the test, and short-acting asthma medications for 12 hours prior to the test.

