Systemic inflammation and immune response – Serum CRP, IgE, periostin, YKL-40 and whole blood eosinophils, neutrophils, and IL-17 will be analyzed from venous blood collected at each assessment day at the end of the visit via antecubital venipuncture by a certified phlebotomist following specified guidelines.²⁶ With the participant sitting in a relaxed position, the upper arm will be occluded to increase the accessibility of the blood vessels. Once a vein is chosen (based on proximity to the surface, size, position and absence of scar tissue and/or pulsation), a sterile 25-gauge needle will be inserted at a 30-degree angle or less to initiate blood draw. Blood will be collected in anti-coagulant-free polypropylene tubes pre labeled with the participant's identification number, date and time, and visit number. After two tubes are collected, the tourniquet will be removed followed by the needle and pressure will be applied to the venipuncture site and held until the bleeding stops. Once collected, the blood will be left to clot for a minimum of 30 minutes followed by centrifuging at 1000g for 10 minutes at 4 degrees Celsius. The serum will be separated into aliquots of 75 µg immediately after centrifuging and then stored at -80 degrees Celsius until analysis. Analysis of inflammatory and immune markers will be completed at the University of Alberta.

Physical activity - Physical activity will be evaluated by step count using a Fitbit activity monitor (Fitbit Inc., San Francisco, CA). Participants will be instructed to wear the monitor on their wrist for 7 days, beginning the morning after Day 2 testing. It will only be removed to shower/bathe and to sleep. Total steps in each 24-hour period will be averaged and used to determine activity levels during the first week of recovery. Low active will be defined as <7,500 steps/day. Somewhat active will be defined as 7,500-9,999 steps/day. Active will be defined as > 10,000 steps/day.²⁷

Pulmonary function – all participants will undergo a full pulmonary function test, according to established clinical guidelines.^{19,20} The expiratory volume in 1 second (FEV₁) responses to

4x100 mg Salbutamol will be evaluated, and an increase in FEV₁ of $\geq 12\%$ and 200 ml will be considered positive for significantly reversible airway constriction.²⁸

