4.1 Confidentiality

Each research participant will be assigned a study ID which will not be associated with any personal identifiable information. All collected study data will be stored either on password protected computer hard drives or in locked filing cabinets.

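### Blinding is ruled out for the whole study, although the recordings behind the main FMD outcome are analysed later and could be read masked to group and visit

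*Combined protocol and SAP*

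**What the plan says.** Under the sub-heading on blinding and avoiding bias, section 3.1.1 has a single sentence: "Due to the nature of the study, blinding will not be applicable". It does not distinguish participants, scanning staff, image readers and analysts.

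The same document describes the primary measurement in two stages. Section 3.3 (Measurements, Endothelial function) says that after cuff release "the blood velocity and the brachial diameter will be monitored for 3 minutes, and later analyzed", and names two software packages. Section 3.1.2 likewise says "FMD data will be analyzed using FDA approved software available from Medical Imaging Applications". Section 3.3 then fixes the outcome: "FMD corrected for SSRH will be considered the main outcome for endothelial function in this study".

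Section 3.4.2 plans three analyses that involve FMD:

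- a comparison of means "for ED visit compared to the control group will be evaluated using an unpaired t-test";
- a repeated-measures ANOVA that "will evaluate the mean differences between each assessment day for the exacerbation group";
- a one-way ANCOVA that corrects FMD for shear rate in all groups, with corrected and uncorrected values both reported.

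The nearest thing to coding is in section 4.1: "Each research participant will be assigned a study ID which will not be associated with any personal identifiable information".

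**The concern.** The reason given for not blinding is the nature of the study. A patient scanned during an emergency visit knows why they are there, and so does the sonographer. Someone who later measures diameters and velocities from a recording need not know. The plan gives no reason for leaving that step open.

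The main outcome is at stake. Reading error unrelated to group and visit adds noise. Reading error that differs by group or visit adds to the very contrasts being tested, and it cannot be removed afterwards without a masked re-read. The introduction argues that inflammation impairs vascular function, so a reader could hold an expectation about which recordings should look worse.

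**Working it through.** There is no stated figure to reproduce. The check sets the relevant sections side by side and counts the assessments affected.

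**1. Can scanning and reading be separated?** Sections 3.1.2 and 3.3 place the analysis after acquisition, in software. That recordings are stored and could be coded is an inference from this. It is a natural one, but the document does not describe export or file handling.

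**2. Which quantities depend on the reading?** Section 3.1.2 defines

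FMD = 100 × (P − B) / B,

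where P is peak hyperemic diameter and B is baseline diameter. A reading error e in P moves FMD by 100 × e / B. Section 3.3 gives velocity during reactive hyperemia as VTI × 60 / HR, and shear stress as 8 × flow / diameter, also accumulated up to the time of peak FMD. Diameter and velocity therefore both enter the corrected outcome. Shear correction does not stand in for masking, because its own inputs are read from the same recordings.

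**3. Does anything elsewhere supply masking?** No section mentions a masked reader, coded recordings, random reading order or a masked analyst. Section 4 assigns data collection to trained study staff and does not say who reads the recordings. The study ID in section 4.1 protects identity; it is not said to conceal group or visit.

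**4. Which contrasts are exposed?**

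| Analysis in section 3.4.2 | What is compared | What the reader must not know |
|---|---|---|
| Unpaired t-test | ED visit against control | Group |
| Repeated-measures ANOVA | Assessment days within the exacerbation group | Visit |
| ANCOVA for shear rate | All groups | Group |

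Masking group alone would leave the second analysis open, so group and visit both need to be hidden. Dates need hiding too, because they can reveal the visit.

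**5. How many assessments?** Section 3.1.1 has FMD at every time point: three for the exacerbation group and two for each control group. Section 3.4.1 plans 44 per group, or 36 before the dropout allowance.

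- At 44 per group: 44 × 3 + 44 × 2 + 44 × 2 = 132 + 88 + 88 = 308.
- At 36 per group: 36 × 3 + 36 × 2 + 36 × 2 = 108 + 72 + 72 = 252.

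Appendix 4 counts 220 visits because it includes only one control group of 44: 132 + 88 = 220. Section 3.4.1 plans two control groups. These are counts of assessments, not files; the number of files per assessment is not stated.

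**The case against.** The strongest reply is that no harm is shown. The document gives no SD for FMD, no reader-error figure and no statement of how automated the software is. If edge detection is largely automatic, a reader has little room to influence the result. No test, sample size or other figure in the plan changes. All of this stands. It limits how strongly the point can be put, but it does not supply a reason for leaving the reading unmasked.

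A reader might go further and infer that the FMD comparisons will be biased, or that their false-positive rate exceeds 0.05 by some definite amount. The document does not support that. Any such rate would rest entirely on an assumed bias, and the document offers nothing from which to choose one.

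Feasibility has limits as well. Masking is only partial if one person both scans and reads, and the document leaves that open; Appendix 4 funds one assistant at 0.25 FTE. Heart rate, needed to compute velocity during reactive hyperemia, may hint that a recording comes from the ED visit. These limits reduce the benefit without removing it.

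**Conclusion.** The point holds in a limited form. The blanket statement in section 3.1.1 is justified for participants and scanning staff, but not for the later reading of diameter and velocity. Up to 308 FMD assessments (252 at 36 per group) would be read with no planned masking, and all three FMD analyses compare groups or visits that the reader may know. The size and direction of any resulting bias are unknown, and the gain from masking falls as the reading becomes more automated.

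The conclusion assumes that recordings are kept in a form that can be coded, and that at least some of the reading needs human judgement. It does not show that the results would be wrong. It is an inexpensive protection of the main outcome that the plan should include.

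**What to change.** Replace the sentence in section 3.1.1 with:

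> Participants and sonographers are not blinded. Stored FMD and velocity recordings are coded to hide group, visit and date, and are read in random order by study staff masked to group and visit, with the key held by another member of the existing team until reading is locked. If the same person scans and reads, this is reported as a limitation.

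The cost is file coding and key-holding by existing staff, plus the protocol wording. No extra visit, procedure, measurement or participant is needed. Reading has to wait until recordings from different groups and visits can be mixed, which may affect the timing of the MSc thesis mentioned in section 7. If heart rate is supplied to the reader, masking of the ED visit may be incomplete.
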